Design and rationale of the Prevention of radial Artery occlusion after Transradial accEss using
NitroglyceriN (PATENS)

NCT03158532

Florianópolis, dec/04/2024

Design and rationale of the Prevention of radial Artery occlusion after Transradial accEss using NitroglyceriN (PATENS)

Abstract

Background

Radial artery occlusion (RAO) is an important access site complications after transradial catheterization (TRC). Acute loss of radial artery patency after TRC is thought be due to a thrombotic process, and a bigger sheath-to-radial-artery ratio could reduce the incidence of RAO. Nitroglycerin acts through the liberation of nitric oxide (NO), which promotes muscle relaxation and vasodilation. Leading to a bigger sheath-to-radial-artery ratio the nitroglycerin administration could help to keep the radial artery patency. The aim is to study if nitroglycerin is superior to placebo concerning incidence of radial artery occlusion, confirmed by vascular Doppler ultrasound, up to 24 hours after catheterization.

Methods/Design

PATENS is a national, multicenter, superiority, 2-by-2 factorial, randomized clinical trial. Two thousand one hundred twenty-eight patients submitted to TRC will be randomized to either nitroglycerin or placebo, administered intra-arterially through the sheath, in two different moments during TRC: after the arterial sheath insertion, at the beginning of procedure, and at the end of the radial procedure, before sheath removal.

Results

The primary efficacy objective is to test the hypothesis that nitroglycerin, dose of 500 mcg, is superior to placebo in decreasing rates of radial artery occlusion on ultrasound Doppler analysis up

to 24 hours after procedures. As secondary objectives, the trial will evaluate the incidence of radial artery occlusion 30 days after catheterization. Enrollment was initiated in August 2017, and the inclusion phase is expected to last until the second half of 2019.

Conclusions

The PATENS trial will help define the role of prophylactic nitroglycerin as a RAO avoidance strategy in patients with submitted to TRC.

Trial registration

ClinicalTrials.gov identifier: NCT03158532

Background

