The use of the transradial approach (TRA) for coronary catheterization has increased over the years, worldwide. Radial artery is nowadays utilized by default for percutaneous coronary procedures in many centers, thanks to the reduced rates of vascular and bleeding complications and easier post-procedural management. The use of TRA also improves patient comfort, saves costs and it has an equivalent procedural success when compared to the femoral approach.

Although it is widely accepted by cardiologists and patients, some problems still exist. One of the major limitations is the development of radial artery spasm (RAS), which can reduce success rates, leading to femoral conversion, and cause significant pain to patients. The incidence of RAS varies between 2% and 34%. Aiming prevent RAS, the use of prophylactic intraarterial vasodilators is

routinely recommended by experts, mainly verapamil or nitroglycerin. Most catheterization laboratories habitually use some medication to prevent RAS, however, it is not a consensus.

Another important complication, often underestimated, is the post-procedural radial occlusion (RAO). Incidence of radial pulse loss has been reported to range from 1% to 12%. The benign nature of such an event has been constantly emphasized due to the dual blood supply to hand from the palmar arch. Mostly, the occurrence of radial occlusion is asymptomatic, symptomatic radial occlusion requiring medical attention occurred in only 0.2% of patients, but hand ischemia caused by RAO has been described. The most important aspect is that once artery is occluded, it can not be used neither as access site for future catheterization, nor be used as a conduit for bypass surgery nor fistula formation in hemodialysis patients. The use of small caliber catheters, adequate dose of heparin administration, immediate sheath removal after procedure, patent hemostasis technique and short time of compressive bandage are the key elements to reduce the risk of artery occlusion. Notably the presence of radial pulse does not exclude radial occlusion due to presence of collateral circulation; it can be more accurately evaluated by absence of antegrade flow in vascular doppler ultrasound. In fact, many operators do not assess radial artery patency before discharge.

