completion, the sheath is initially pulled by approximately 2 to 3 cm. The device is applied to the patient with the green marker (located in the center of the larger balloon) positioned exactly at the puncture hole to aid in the location, visualization and control of possible bleeding. The balloon is inflated with an adequate syringe injecting 15 ml of air with simultaneous and total sheath removal, resulting in the absence of active bleeding. If bleeding occurs, additional 3 ml of air is injected to obtain complete hemostasis. The device is then slowly deflated to the lowest allowable volume (minimum 7 ml) while maintaining hemostasis. If bleeding occurred, 1 ml of air was reintroduced from the bleeding point. Radial artery patency was evaluated utilizing plethysmographic and pulse oximetry evaluation, with sensor placed over the thumb or index finger, and occlusion (manual pressure) of the ulnar artery. Absence of plethysmographic waveform is indicative of interruption of radial artery flow. After 1 hour post diagnostic procedure or 2 hours post intervention, 3 ml of air is removed every 15 minutes. If bleeding occurs during any stage of device removal, the volume of air needed for hemostasis is again injected, restarting the deflation process 60 minutes later. When all the air is removed, and there is no bleeding, the device is removed and the access site is covered with a simple dressing. Dressing should not encircle the entire wrist.

Statistical analysis

The primary analysis of the study is a superiority comparison between the use of nitroglycerin to decrease RAO, in all randomized patients, based on the intention-to-treat principle.

Using our primary end point to estimate the sample size, we suppose to have a 30% reduction in RAO for each trial intervention, considering potential interaction between them. Estimating RAO prespecified in the primary outcome of approximately 11.7% without use of nitroglycerin, with an alpha level of 0.05 and a beta level of 0.20, the minimum estimated sample size per group was established as 1064 individuals. As we do not expect any subsequent loss of follow-up due to the short primary evaluation, the enrollment of 2128 patients would provide sufficient power to the

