study. Continuous variables will be described as means and standard deviation and compared using Student's t -test for normally distributed variables or assessed using Mann-Whitney test when not normally distributed. Categorical variables are expressed as frequencies and group percentage and will be compared with the chi-square or Fisher's exact tests. To test the interaction between interventions, we used a multivariable logistic-regression model that included the two randomized treatments and their interaction as parameters. In the analysis of the primary and secondary end points, a two-tailed p value of less than 0.05 will be considered statistically significant. No prespecified interim analysis will be performed. All analyses will be performed using SPSS version 22 (SPSS Inc., Chicago, Illinois).

Discussion

Cardiac catheterization is a common procedure and is need in many clinical scenarios and many times repeated procedures are need. The use of TRA is increasing aiming to improve patient comfort, save costs and reduce rates complications. This implies that the occurrence of RAO should be considered because, once it's occurred, it is impossible to use radial access for future catheterization. In most cases RAO occurs promptly after the procedure and up to 50% of patients have spontaneous recanalization of the artery within 1 month. A palpable pulse does not exclude the diagnosis of RAO: collateral blood flow may supply the periphery of the radial artery distally to the occlusion, giving a false impression of radial artery patency. Therefore, RAO can often be undiagnosed. Radial artery patency is better evaluated with clinical testing as the reverse Barbeau's test and with Doppler ultrasonography. Many interventions are suggested to reduce the risk of RAO, mainly anticoagulation, patent hemostasis and a bigger sheath-to-radial-artery ratio. Although nitroglycerin promotes vasodilation and thus improves the sheath-to-radial-artery ratio, no recommendation is done to its routinely use. Handling confounding factors such as anticoagulation and hemostasis, this test has an ideal design to address the question of whether routine use of the

nitroglycerin approach is superior to not use with respect to the occlusion occurrence, including possible predictors.

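### No effect estimate or confidence interval is planned for radial artery occlusion, and 1064 per group gives about 77% power (about 70% on the factorial margins), not 80%

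*Combined protocol and SAP*

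**What the plan says.** All of the relevant text is in the Statistical analysis section of the combined protocol and SAP.

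- **Analysis of RAO.** RAO is a yes/no outcome (Doppler, up to 24 hours), so it falls under the rule for categorical variables: "Categorical variables are expressed as frequencies and group percentage and will be compared with the chi-square or" Fisher's exact tests. The decision criterion is that "a two-tailed p value of less than 0.05 will be considered statistically significant".
- **Model.** A logistic regression holds the two randomized treatments and their interaction. Its stated purpose is to test that interaction. The section does not say that treatment effects on RAO will be estimated or reported from it.
- **Estimates.** No risk ratio, risk difference, odds ratio or confidence interval is named for RAO anywhere in the document.
- **Sample size.** The effect assumption is: "we suppose to have a 30% reduction in RAO for each trial intervention", with potential interaction said to be considered. The event rate is given as: "Estimating RAO prespecified in the primary outcome of approximately 11.7% without use of nitroglycerin". The calculation is made "with an alpha level of 0.05 and a beta level of 0.20" and gives a minimum of 1064 per group. No loss to follow-up is expected, and 2128 patients are said to be enough.

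**The concern.** A test result and two percentages do not by themselves say which effects the data rule out. The Abstract states the purpose as follows: "The PATENS trial will help define the role of prophylactic nitroglycerin as a RAO avoidance strategy". If the result is not significant, readers will want to know whether a 30% reduction has been excluded or remains possible. The plan names no quantity that answers this and does not say how such a result will be read.

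The power statement bears on the same question, because it tells the reader how surprising a non-significant result would be if the drug worked as assumed. If true power is below the claimed 80%, that result is more likely under a real 30% benefit than the plan implies. In a factorial trial there is a further issue. Half of each comparison's control group receives nitroglycerin at the other time point, so the rate without nitroglycerin need not be the control rate of the comparison.

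**Working it through.** **Inputs from the Statistical analysis section.** Rate without nitroglycerin 11.7%; reduction 30%, read as relative because an absolute reduction of 30 points is impossible; alpha 0.05, two-tailed; beta 0.20; 1064 per group, 2128 in total. Allocation of 1:1 is inferred from 2 × 1064.

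**1. The plan's own sample size.** Treated rate = 0.117 × 0.70 = 0.0819; mean rate = 0.09945.

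n = [1.96·√(2p̄(1−p̄)) + 0.8416·√(p₁(1−p₁)+p₂(1−p₂))]² / (p₁−p₂)²

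= [1.96 × 0.4232 + 0.8416 × 0.4225]² / 0.0351² ≈ **1140 per group**.

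Other standard two-sided forms give 1138 (unpooled), 1133 (arcsine) and 1197 (continuity-corrected). One-sided forms give 898, or 954 with correction. None returns 1064.

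**2. Power at 1064 per group.**

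z = [0.0351 × √1064 − 1.96 × 0.4232] / 0.4225 = 0.747, so power is **about 77%**.

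**3. Power on the factorial margins.** Assume that each dose multiplies the RAO risk by 0.70 independently of the other, with equal cells. The four cell rates are:

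| | No end dose | End dose |
|---|---|---|
| No start dose | 11.7% | 8.19% |
| Start dose | 8.19% | 5.733% |

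- Control margin: (11.7 + 8.19)/2 = 9.945%.
- Active margin: (8.19 + 5.733)/2 = 6.96%.
- z = [0.029835 × √1064 − 1.96 × 0.3934] / 0.3928 = 0.514, so power is **about 70%**. Reaching 80% would take 1364 per margin.

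**4. What a non-significant result can mean.** The interval is the Wald 95% CI on the log risk ratio, with 1064 per group:

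SE = √[(1−p₁)/(1064p₁) + (1−p₂)/(1064p₂)]; CI = RR × exp(±1.96·SE)

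| Observed rates | RR | SE | 95% CI | Includes 0.70? |
|---|---|---|---|---|
| 11.7% vs 11.7% | 1.00 | 0.119 | 0.79 to 1.26 | No |
| 11.7% vs 9.945% | 0.85 | 0.125 | 0.67 to 1.09 | Yes |
| 5% vs 5% (assumed rate) | 1.00 | 0.189 | 0.69 to 1.45 | Yes |

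All three are non-significant; the middle row has p = 0.19. The first two rows share the planning rate, so the contrast between them does not need 11.7% to be wrong. With equal observed rates, the interval stops excluding 0.70 below a rate of about 5.4%.

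**5. Sensitivity to the rate.** These no-nitroglycerin rates are assumptions, not figures from the documents. Each margin rate is the assumed rate × 0.85 (control) or × 0.595 (active).

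| No-nitroglycerin rate | Margins | Power, 1064 per margin |
|---|---|---|
| 8% | 6.80% vs 4.76% | about 52% |
| 5% | 4.25% vs 2.975% | about 35% |
| 3% | 2.55% vs 1.785% | about 23% |

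**The case against.** **The counts are reported, so nothing is lost.** This is right as far as it goes. For a binary outcome in two groups, the frequencies determine the risk ratio, the risk difference and their intervals. A reader might infer that the trial could not tell a true null from an uninformative result; the documents do not support that. The gap is in prespecification: which measure is primary, and that the interval will guide interpretation. The logistic model would also yield coefficients, but with the interaction term in it they are not the two marginal effects, and its stated use is the interaction test.

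**The plan does not say that p ≥ 0.05 means no role for nitroglycerin.** Correct. It says only when a result is significant, and is silent on how to read one that is not. A reader might infer a dismissal rule, but none is written.

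**The planning rate.** A reader might infer that 11.7% is too high, because the Background says: "Incidence of radial pulse loss has been reported to range from 1% to 12" percent. That range is for pulse loss. The endpoint is Doppler occlusion, and the Background itself warns that a palpable pulse does not exclude it. Preventive measures applied to all arms might lower the rate, but the source of 11.7% is not given and may already reflect them.

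**The shortfall may be rounding.** A treated rate of 8.1% gives 1080 per group, and 8.0% with continuity correction gives 1071, both close to 1064. Those rates imply reductions of about 31% to 32%, so the stated 30% still does not carry 80% power.

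**The 30% is a sizing assumption, not a declared smallest worthwhile effect.** True. A formal three-way decision rule would be a matter of preference. Saying whether the interval includes the planned effect needs no such declaration.

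**Conclusion.** The point holds on two counts.

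- **Estimation.** No effect measure or interval is prespecified for the primary endpoint. At the plan's own rate and sample size, non-significant results can either exclude the planned 30% reduction or be compatible with it. This is a shortfall in prespecified reporting and interpretation. The significance test itself is not invalid.
- **Power.** On the stated inputs, power is about 77% for a single comparison at 11.7% against 8.19%, 3 points below the claim and 76 patients per group short (1140 − 1064). On the factorial margins it is about 70%. The margin figure assumes 1:1 allocation, a 30% reduction from each dose acting independently on the risk-ratio scale, and 11.7% as the rate in the double-placebo cell, which is how the plan words it. The plan says that it considered potential interaction but shows no allowance for it.

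Nothing here shows that 11.7% is wrong. Power at lower rates is illustrative only.

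**What to change.** In the Statistical analysis section:

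1. **Primary result.** For each randomized dose (start of procedure, end of procedure), report the risk ratio and risk difference for RAO with 95% confidence intervals as the primary result, alongside the existing chi-square or Fisher test. State that a non-significant result will be interpreted from the interval, noting whether it includes the planned 30% reduction (risk ratio 0.70).
2. **Power statement.** Replace the 80% claim, and the sentence that 2128 patients are enough, with about 77% for a single comparison at 11.7% and about 70% for the factorial margins, giving the assumptions. If lower rates are shown, label them as assumptions: margin power of about 52%, 35% and 23% at no-nitroglycerin rates of 8%, 5% and 3%.

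The cost is a few lines of text and a slightly less favourable power statement. No new data are needed, and the test and the 0.05 threshold stay as they are.
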